4.3.8 Baseline Magnetic Resonance Imaging Data

The following characteristics of baseline MRI data will be analyzed:

- Volume of T2 lesions at baseline: summary statistics, including mean, median, SD, minimum, and maximum
- Number of T2 lesions at baseline: summary statistics, including mean, median, SD, minimum and maximum, and number and percentage of patients in each category (0–5, 6–9, and $>$ 9 T2 lesions at baseline)
- Number of gadolinium (Gd)-enhancing T1 lesions at baseline: summary statistics, including mean, median, SD, minimum and maximum, and number and percentage of patients in each category (0, 1, 2, 3, and \geq 4 Gd-enhancing T1 lesions at baseline)

- Normalized brain volume at baseline: summary statistics, including mean, median, SD, minimum, and maximum
- White matter volume at baseline: summary statistics, including mean, median, SD, minimum, and maximum
- Cortical grey matter volume at baseline: summary statistics, including mean, median, SD, minimum, and maximum
- Un-enhancing T1-lesion volume at baseline: summary statistics, including mean, median, SD, minimum, and maximum
- Number of T1 hypo-intense lesions (black holes) at baseline: summary statistics, including mean, median, SD, minimum, and maximum

A listing of MRI assessments at baseline will be provided.

4.4 OUTCOME ANALYSIS

No hypothesis testing will be performed.

For immunology endpoints, pre-immunization levels are those obtained immediately prior to administration of a vaccine.

Patients with missing immunology assessment data will not be included in the calculations. No missing data imputation methods will be applied.

For immunology endpoints, except where stated, tabular presentations will show Group A (Groups A1 and A2 combined) and Group B.

Summaries will be presented for the OC Population only.

4.4.1 Primary Immunology Endpoint

The primary outcome measure is the proportion of patients in Groups A and B with a positive response (IgG) to TT adsorbed vaccine measured 8 weeks after TT booster vaccine administration. Positive response is defined as follows:

- For patients with pre-immunization tetanus antibody titers <0.1 IU/mL, a positive response to the booster TT immunization is defined as an antibody titer ≥ 0.2 IU/mL measured 8 weeks after immunization.
- For patients with pre-immunization tetanus antibody titers ≥ 0.1 IU/mL, a positive response to the booster TT immunization is defined as a 4-fold increase in antibody titers measured 8 weeks after immunization compared with pre-immunization levels.

The number and proportion of patients with a positive response to TT adsorbed vaccine will be presented by treatment group. The difference between treatment groups A and B in positive response rates and the associated 95% CI will also be presented using a normal approximation method.

Levels of anti-tetanus antibody in patients in Groups A and B measured 8 weeks after a booster TT vaccine administration will be summarized descriptively by treatment, showing the following summary statistics:

- Number and percentage of patients with values \leq LLQ
- Number and percentage of patients with values $>$ LLQ
- Geometric mean of known values $>$ LLQ
- 95% CI for geometric mean of known values $>$ LLQ, calculated using a normal approximation method on the log scale and then back-transformed to the original scale
- Geometric mean of all nonmissing values, imputing $LLQ \div 2$ for values \leq LLQ
- 95% CI for geometric mean of all nonmissing values, imputing $LLQ \div 2$ for values \leq LLQ, calculated using a normal approximation method on the log scale and then back-transformed to the original scale
- Median of known values $>$ LLQ
- Median of all nonmissing values, imputing $LLQ \div 2$ for values \leq LLQ

To aid comparison back to pre-vaccination levels, the following pre-vaccination summary statistics will also be included in the tabular summary at 8 weeks:

- Geometric mean of known pre-vaccination values $>$ LLQ
- Geometric mean of all nonmissing pre-vaccination values, imputing $LLQ \div 2$ for values \leq LLQ

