3. STUDY DESIGN

3.1 DESCRIPTION OF STUDY

This Phase IIIb, multicenter, randomized, open-label study is designed to evaluate immune response to vaccines after administration of a dose of OCR (i.e., a dual infusion of OCR 300 mg on Day 1/Week 1 [Dose 1 Infusion 1] and Day 15/Week 2 [Dose 1 Infusion 2]) in patients with RMS.

Following screening, approximately 100 adult patients will be randomized into Groups A and B (2:1; active:control) to compare responses to immunization. Patients in Group B are to receive immunization with TT-containing adsorbed vaccine, 23-PPV, influenza vaccine, and repeated administration with KLH. Group B patients will not receive OCR but will remain on no MS-specific disease-modifying therapy (DMT) or continue with IFN- β treatment until optional OCR treatment at the end of the Immunization Study Period.

Patients in Group A are to first receive OCR (Day 1/Week 1 [Dose 1 Infusion 1] and Day 15/Week 2 [Dose 1 Infusion 2]), and 12 weeks post-OCR treatment, are to receive a similar immunization course to Group B. Group A will be further subdivided into two groups to evaluate the effectiveness of a booster 13-PCV vaccination or of influenza vaccination.

For the primary objective and for secondary objectives 1 and 3 (see Sections [2.1](#) and [2.2](#), respectively), Group A (active) will be compared with Group B (control).

To determine the outcomes of secondary objectives 2 and 4, patients in Group A will be split into two groups with 50% of patients in each group (Groups A1 and A2). Patients will be assigned to either Group A1 or A2:

- Group A1 will receive booster 13-PCV (approximately 33 patients)
- Group A2 will receive the influenza vaccine (approximately 33 patients but a minimum of 30 patients).

A minimum of 30 patients will be assigned to Group A2 during the first influenza season. If a minimum of 30 patients (a maximum of 33) are assigned to Group A2 and receive the first year's influenza vaccine, all remaining patients in Group A will be assigned to

Group A1 and receive the 13-PCV booster. If less than 30 patients have been assigned to Group A2 during the first influenza season, further patients assigned to Group A2 will have influenza vaccine visits during the subsequent influenza season (i.e., when the next year's vaccine becomes available).

The primary and secondary humoral immunity and immunophenotyping outcomes are to be measured by flow cytometry and quantitative Ig measurements.

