2.3 DETERMINATION OF SAMPLE SIZE

For the positive response to TT-containing adsorbed vaccine measured 8 weeks after the administration of vaccine, if both the control and active (ocrelizumab) groups have 70% response rates, the expected half-width of the resulting 95% CI of the difference of 2 response rates is 0.201. To achieve this precision, approximately 100 patients will be enrolled using a 2:1 randomization ratio into active ocrelizumab (Group A) and control (Group B) groups.

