Group A1: Patients in Group A1 receive the 23-PPV vaccine at Week 16 and also the 13-PCV booster vaccination 4 weeks later at Week 20. All 23 serotypes are assessed immediately prior to 23-PPV vaccination at Week 16, again prior to the 13-PCV “booster” 4 weeks later at Week 20, and then again 4 weeks after that at Week 24.

Group A2: Patients in Group A2 receive the 23-PPV vaccine at Week 16, but do not receive the 13-PCV “booster”. All 23 serotypes are assessed immediately prior to 23-PPV vaccination at Week 16, again 4 weeks later at Week 20 and again 4 weeks after that at Week 24.

Group B: Patients in Group B follow a similar schedule to Group A2, but earlier in the study. They receive the 23-PPV vaccine at Week 4, and do not receive the 13-PCV “booster”. All 23 serotypes are assessed immediately prior to 23-PPV vaccination at Week 4, again 4 weeks later at Week 8 and again 4 weeks after that at Week 12.

Summaries will show the following groups separately: Group A1, Group A2, Group A (Groups A1 and A2 combined), and Group B. Pairwise between-group comparisons will show:

- Group A1 versus Group A2
- Group A1 versus Group B
- Group A2 versus Group B
- Group A (A1 and A2 combined) versus Group B

Note that the first 3 of the 4 comparisons above, which involve treatment groups A1 and A2 separately, should be interpreted with some caution, since patients were not assigned to these 2 treatment groups randomly (patients were randomized to Group A or

Group B, and within Group A were non-randomly assigned to Group A1 or A2, based on seasonality considerations).

A positive response against a serotype is defined as developing either a 2-fold increase in level or a > 1 $\mu\text{g/mL}$ rise in level, compared with pre-immunization levels.

At 4 weeks after the 23-PPV vaccine, the number and proportion of patients in Groups A1, A2, A (A1 and A2 combined), and B with a positive response (as defined above) against each of the 23 serotypes will be presented. For the same 4 pairwise between-group comparisons described earlier in this section, pairwise between-group differences in positive response rates and the associated 95% CI will also be presented for each serotype, using a normal approximation method.

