At 4 weeks after the 23-PPV vaccine, the number and proportion of patients in Groups A1, A2, A (A1 and A2 combined), and B with positive responses (as defined above) against at least 2 of the 23 serotypes will also be presented. For the same 4 pairwise between-group comparisons described earlier in this section, pairwise between-group differences in response rates and the associated 95% CI will also be presented, using a normal approximation method.

At 4 weeks after the 23-PPV vaccine, the number and proportion of patients in Groups A1, A2, A (A1 and A2 combined), and B with positive responses (as defined above) against at least 50% of the serotypes (≥ 12 of 23) will also be presented. For the same 4 pairwise between-group comparisons described earlier in this section, pairwise between-group differences in response rates and the associated 95% CI will also be presented, using a normal approximation method.

At 8 weeks after the 23-PPV vaccine (which is 4 weeks after Group A1 patients received the 13-PCV booster), the number and proportion of patients in Groups A1, A2, A (A1 and A2 combined), and B with a positive response (as defined above) against each of the 23 serotypes will be presented. For the same 4 pairwise between-group comparisons described earlier in this section, pairwise between-group differences in positive response rates and the associated 95% CI will also be presented for each serotype, using a normal approximation method.

Levels of anti-pneumococcal antibodies ($\mu\text{g/mL}$) against each of the 23 different serotypes in patients in Groups A1, A2, A (A1 and A2 combined), and B measured 4 weeks and 8 weeks after administration of 23-PPV (which is 4 weeks after Group A1 patients received the 13-PCV booster) will be summarized descriptively by group using the same summary statistics as presented in Section 4.4.1 for the primary immunology endpoint.

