4.4.2.4 Influenza Vaccine Response

Between-group comparisons of influenza vaccine response require comparison of Groups A2 and B. As noted above in Section 4.4.2.2, comparisons between Groups A2 and B should be interpreted with some caution, since patients were not assigned to Group A2 randomly (patients were randomized to Group A or B, and within Group A were non-randomly assigned to Group A1 or A2, based on seasonality considerations).

The number and percentage of patients in Groups A2 and B who achieve seroprotection, defined as specific HI titers >40 at 4 weeks after vaccination, will be presented by treatment group. The difference between Groups A2 and B in seroprotection rates, and the associated 95% CI will also be presented using a normal approximation method.

The number and percentage of patients in Groups A2 and B who achieve a 2-fold increase in specific HI titers at 4 weeks after vaccination will be presented by treatment group. The difference between Groups A2 and B in the proportion of patients achieving a 2-fold increase, and the associated 95% CI will also be presented using a normal approximation method.

The number and percentage of patients in Groups A2 and B who achieve a 4-fold increase in specific HI titers at 4 weeks after vaccination will be presented by treatment group. The difference between Groups A2 and B in the proportion of patients achieving a 4-fold increase, and the associated 95% CI will also be presented using a normal approximation method.

The number and percentage of patients in Groups A2 and B who achieve seroconversion at 4 weeks after vaccination, defined as a pre-vaccination antibody titer <10 and a HI titer >40 at 4 weeks after vaccination, will be presented by treatment group. The difference between Groups A2 and B in seroconversion rates, and the associated 95% CI will also be presented using a normal approximation method.

Strain-specific GMTs in patients in Groups A2 and B measured 4 weeks after vaccination will be summarized descriptively by treatment group using the same summary statistics as presented in Section 4.4.1 for the primary immunology endpoint.

Strain-specific GMT ratio (post-vaccination:pre-vaccination) in patients in Groups A2 and B will be summarized descriptively by treatment group; summary statistics calculated will include mean, median, SD, minimum, and maximum.

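### The normal-approximation CI for differences in pneumococcal and influenza response rates can under-cover, or collapse to zero width, when both groups are near 0% or 100%

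*SAP*

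**What the plan says.** SAP 4.4.2.2 defines response for each of 23 pneumococcal serotypes, at 4 and at 8 weeks after 23-PPV, over four pairwise comparisons (A1 v A2, A1 v B, A2 v B, A v B). For these, "the associated 95% CI will also be presented for each serotype, using a normal approximation method". For the composites of at least 2 and at least 12 of 23 serotypes, "pairwise between-group differences in response rates and the associated 95% CI will also be presented, using a normal approximation method".

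SAP 4.4.2.4 does the same for influenza in Groups A2 and B: "The difference between Groups A2 and B in seroprotection rates, and the associated 95% CI will also be presented using a normal approximation method". It repeats this for the 2-fold rise, the 4-fold rise and seroconversion. The tetanus differences at 8 weeks (SAP 4.4.1) and 4 weeks (SAP 4.4.2.1) use the same method: "the associated 95% CI will also be presented using a normal approximation method".

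On size, SAP 2.3 says that "approximately 100 patients will be enrolled using a 2:1 randomization ratio", which makes Group A about 67 and Group B about 33. Protocol 3.1 puts A1 and A2 at about 33 each, with a minimum of 30 in A2. Denominators can be smaller, because SAP 4.1.2 analyzes only patients who complete the Immunization Study Period and SAP 4.4 drops missing assessments. SAP 4.4 also rules out hypothesis testing. Neither document names a score, exact or continuity-corrected interval, or says what to do when a cell is 0% or 100%.

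**The concern.** The Wald interval estimates its variance from the observed proportions. Near 0% or 100% that estimate is too small, and at exactly 0% or 100% it is zero.

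Some endpoint definitions lean towards those boundaries. A response to only 2 of 23 serotypes, where either a 2-fold increase or a rise above 1 µg/mL counts, is prone to a ceiling. Seroconversion that needs a pre-vaccination titer below 10 and a post-vaccination titer above 40 is prone to a floor if every patient stays in the denominator. With many serotypes, some are likely to sit at an edge.

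Because nothing is tested, the CIs are the only inferential output. An interval of 0 to 0 from 100 patients, or a nominal 95% interval that covers about 81% of the time, misstates the precision of that output.

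**Working it through.** **The plan's own figure.** SAP 2.3 gives an expected half-width of 0.201 "if both the control and active (ocrelizumab) groups have 70% response rates". The unpooled Wald half-width is 1.96 × √[p₁(1−p₁)/n₁ + p₂(1−p₂)/n₂].
- At 67:33: 1.96 × √(0.21/67 + 0.21/33) = 0.191.
- At 60:30: 1.96 × √(0.21/60 + 0.21/30) = 0.2008.

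So 0.201 is not reproduced at 100 patients. It matches the plain Wald formula at 90, an allowance that the documents do not state. This supports the Wald reading but does not prove it.

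**Number of intervals.** SAP 4.4.2.2 alone yields 4 × (23 + 1 + 1 + 23) = 192 intervals. Three of the four comparisons, hence 144 intervals, involve A1 or A2. Influenza adds four per strain.

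**Coverage.** Every pair of binomial outcomes was enumerated, and the probability of those whose interval contains the true difference was summed. All rates except 70% are assumptions.

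| Situation | n₁ v n₂ | True rates | Wald | Newcombe |
|---|---|---|---|---|
| Planned primary | 67 v 33 | 70% v 70% | 0.940 | 0.949 |
| Mid-range, small groups | 33 v 34 | 70% v 70% | 0.942 | 0.949 |
| One extreme | 67 v 33 | 60% v 95% | 0.945 | 0.954 |
| One extreme | 33 v 33 | 70% v 98% | 0.925 | 0.967 |
| One extreme | 67 v 33 | 2% v 20% | 0.916 | 0.962 |
| Both extreme | 67 v 33 | 95% v 98% | 0.938 | 0.980 |
| Both extreme | 33 v 34 | 95% v 95% | 0.966 | 0.990 |
| Both extreme | 67 v 33 | 99% v 95% | 0.813 | 0.986 |
| Both extreme | 67 v 33 | 2% v 5% | 0.812 | 0.975 |
| Both extreme | 33 v 33 | 95% v 99% | 0.812 | 0.995 |
| Both extreme | 33 v 33 | 90% v 100% | 0.852 | 0.996 |
| Both extreme | 33 v 33 | 1% v 10% | 0.845 | 0.988 |
| Opposite extremes | 33 v 33 | 5% v 95% | 0.843 | 0.954 |
| Opposite extremes | 67 v 33 | 5% v 95% | 0.880 | 0.946 |

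Averaged over both rates between 90% and 99%, Wald covers 0.905 at 33 v 34 and 0.898 at 30 v 33; Newcombe covers 0.983 and 0.985. Isolated pairs hard against the ceiling go lower than the table shows (grid minima 0.54 to 0.60), but neighboring pairs recover, so those minima do not describe the method in general.

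**Zero width.** This needs both groups at exactly 0% or 100%. With 67/67 v 33/33 the Wald variance is 0 and the interval is 0 to 0. For Newcombe, the Wilson lower limits are 67/(67 + 3.84) = 0.946 and 33/(33 + 3.84) = 0.896. The interval therefore runs from −(1 − 0.946) = −0.05 to 1 − 0.896 = 0.10. With 0/33 v 34/34, Wald gives −1 to −1 and Newcombe −1.00 to −0.85. If both true rates are 98% at 33 v 34, the chance of a zero-width interval is about 0.98⁶⁷ = 0.26; at 95% it is about 0.95⁶⁷ = 0.03.

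**The case against.** **The primary is fine.** Because the wording appears first in SAP 4.4.1, a reader might infer that the primary result is unreliable. It is not: 70% is the only rate in the plan, and coverage there is 0.94. This stands.

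**81% is not typical.** A reader might take it as the usual coverage at extreme rates. Coverage oscillates, and pairs close to the poor ones do well (95% v 98%, 0.938). B-cell depletion should also pull Group A away from Group B, which often leaves only one group extreme and costs little. This stands too. But poor pairs also occur in the direction that depletion implies, such as 90% v 100% or 1% v 10%.

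**Wald is not written.** A continuity-corrected interval also fits the SAP's words and never has zero width. The collapse therefore belongs to the natural reading and is not certain. Correction is only a partial remedy: at 99% v 95% (67 v 33) it still covers about 0.815. For 67/67 v 33/33 it gives ±(1/67 + 1/33)/2 = ±0.023, much narrower than Newcombe.

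**Little depends on it.** There is no test, margin or decision rule. The SAP shows responder counts beside each difference, so a reader would see 67/67 v 33/33. This is the strongest point and sets the severity.

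**Not all influenza endpoints are affected.** Only the four proportions are; the geometric mean titers and their ratio do not use this interval.

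**Conclusion.** The concern holds for the pneumococcal and influenza response-rate differences, at low severity. Small groups alone cost about one point of coverage, and one extreme group usually leaves about 0.92 to 0.96. The real loss, to about 0.81 to 0.88 for some pairs, needs both rates near 0% or 100%. Zero width needs both groups exactly there.

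This rests on two assumptions: that the normal approximation means the uncorrected, unpooled Wald interval, and that some serotype or influenza rates turn out extreme. The documents give no such rates. Protocol 5.1.1.6 reports only that responses were lower on ocrelizumab.

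The documents do not support the wider inference that the tetanus primary, or any trial conclusion, is compromised. What is affected is how honestly precision is reported for the secondary proportions.

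**What to change.** In SAP 4.4.1 to 4.4.2.4, replace the reference to a normal approximation for differences in proportions with a named interval: Newcombe hybrid score or Miettinen-Nurminen. Either gives a usable result at 0% and 100%, so no separate rule is needed. The log-scale intervals for geometric means stay as they are.

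The cost is a wording change and a standard software option. Protocol 5.1.1.6 shows that results of the Immunization Study Period already exist, so the tables concerned would have to be rerun.

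Some intervals become slightly wider or asymmetric, and near the boundary Newcombe is somewhat conservative (0.97 to 0.995 at several pairs above). It is not perfect either: at 2% v 98% with 33 v 33 it covers 0.879, against 0.734 for Wald. The primary is essentially unchanged: 46/66 v 24/34 gives −0.198 to 0.180 by Wald and −0.182 to 0.185 by Newcombe.

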4.7.9.2 Immunization Response Laboratory Assessments

Tetanus Antibody Assay

The tetanus antibody test will be used to measure anti-tetanus antibody levels in human serum samples. The tetanus antibody test is an ELISA that uses TT as a capturing reagent and alkaline phosphatase-conjugated anti-human IgG (γ) for detection. Results are reported in IU/mL.

Pneumococcal Antibody Assay (for 23-PPV and 13-PCV)

A bead-based multi-analyte immunodetection (MAID) assay using Luminex Magplex microspheres will be used to measure anti-pneumococcal IgG levels in human serum samples. The pneumococcal antibody assay is a fluoroimmunoassay that uses a Luminex Multiplex platform. Purified capsular polysaccharides isolated from 23 serotypes of *S. pneumonia* covalently attached to microbeads will be used as capturing reagent (IgG levels to serotype 6A, specific to 13-PCV cannot be tested in this assay). Results are reported in microgram of IgG/mL.

KLH Antibody Assay

A KLH antibody assay will be used to measure anti-KLH antibody levels (IgG and IgM) in human serum samples. The KLH antibody assay is an ELISA format using KLH as the plate coating and anti-human IgG-horseradish peroxidase for detection. Results are reported in titer units.

Influenza Vaccine

The hemagglutination inhibition (HAI) assay will be used to measure anti-influenza antibody levels in human serum samples. Results are reported in HAI units.

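### The SAP halves a result equal to the LLQ and drops it from the above-LLQ summaries; where results tie at the limit, as HI titers may, this distorts the descriptive GMTs and medians

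*SAP*

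**What the plan says.** SAP 4.4.1 sorts antibody levels into those at or below the LLQ and those above it. It then asks for two families of summaries. One covers everyone: "Geometric mean of all nonmissing values, imputing" LLQ/2 for every value at or below the LLQ, with a matching median. The other covers only the upper part: "Geometric mean of known values $>$ LLQ", again with a median. SAP 4.3.7 uses the same split and the same substitution for pre-vaccination levels, including the strain-specific influenza GMTs in Groups A2 and B.

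SAP 4.4.2.4 extends the rule to influenza after vaccination: the strain-specific GMTs are to be "summarized descriptively by treatment group using the same summary statistics as presented in Section 4.4.1 for the primary immunology endpoint". The same section makes seroconversion depend on a low starting titer, "defined as a pre-vaccination antibody titer <10 and a HI titer >40 at 4 weeks after vaccination".

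On the assay, Protocol 4.7.9.2 says only "Results are reported in HAI units". Neither document states the LLQ of the HI assay or of any other assay, or how a result below the limit is stored in the data. Protocol 4.7.9 leaves the reporting of central-laboratory results to the Laboratory Manual.

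**The concern.** The LLQ is the lowest level that the assay can quantify, so a result equal to it has been measured. The SAP puts it on the unquantified side. In the all-values summaries it becomes LLQ/2, the same as a result that could not be measured. In the above-LLQ summaries it disappears. The counts use the same cut, so the reader of the table cannot recover it.

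For a continuous ELISA this hardly matters, because exact ties at the limit are rare. It can matter for an assay read in steps. HI titers are the likely case, and the seroconversion cut-off of <10 suggests, without saying so, that 10 is the lowest measured titer. If so, a titer of 10 is distinct from <10 for seroconversion but is merged with it, at 5, in the GMT.

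At stake is the accuracy of the descriptive GMTs and medians, and their comparability between groups or timepoints with different shares of results at the limit.

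**Working it through.** The documents give no figure to reproduce on this point: no LLQ and no expected titers. The sample-size figure for tetanus response does not enter.

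**Inputs**
- Substitution rule: LLQ/2 for values ≤ LLQ (SAP 4.3.7, 4.4.1), applied to influenza GMTs (SAP 4.4.2.4).
- Group sizes: about 33 in A2, minimum 30 (Protocol 3.1); about 33 in B (100 patients at 2:1, Protocol 6.1).
- Assumed: HI LLQ of 10; readings 10, 20, 40 and so on; underlying titers log2-normal with SD 1.5, 2 or 2.5 log2 units.

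**Step 1: one group.** Compare the SAP rule with one that keeps a result equal to the limit L. Each such result falls from L to L/2, which is 1 unit on the log2 scale. If a share f of the group is exactly at L, the mean log2 titer falls by f, so the GMT is multiplied by 2^(−f):

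| f | 1/33 | 5% | 10% | 20% | 30% |
|---|---|---|---|---|---|
| factor | 0.979 | 0.966 | 0.933 | 0.871 | 0.812 |

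The all-values median moves only if a middle value lies at L. The above-LLQ geometric mean moves the other way, since it loses its lowest measured results.

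**Step 2: two groups or two timepoints.** The A2:B ratio of GMTs is multiplied by 2^(−(f_A2 − f_B)). A difference of +5 points gives 0.966, +10 gives 0.933, +20 gives 0.871, −5 gives 1.035 and −10 gives 1.072. For a post:pre ratio of two GMTs that both use the substitution, 20% at the limit before and 5% after gives 2^0.15 = 1.11; the reverse gives 2^(−0.15) = 0.90. These shares are illustrations.

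**Step 3: which group has the larger share at the limit?** With underlying geometric mean G and m = log2(G/10),

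P(titer = 10) = Φ((1 − m)/SD) − Φ(−m/SD).

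At SD 2:

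| G | P(<10) | P(=10) | GMT, SAP rule | GMT, 10 kept | factor |
|---|---|---|---|---|---|
| 3 | 0.807 | 0.107 | 5.8 | 6.2 | 0.929 |
| 5 | 0.691 | 0.150 | 6.7 | 7.4 | 0.901 |
| 14 | 0.404 | 0.197 | 11.3 | 13.0 | 0.872 |
| 20 | 0.309 | 0.191 | 14.8 | 16.9 | 0.876 |
| 40 | 0.159 | 0.150 | 27.3 | 30.3 | 0.901 |
| 80 | 0.067 | 0.092 | 54.2 | 57.8 | 0.938 |
| 160 | 0.023 | 0.044 | 110.3 | 113.8 | 0.970 |

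The share at the limit peaks near G = 14 and falls on both sides. Two pairs show the consequence:
- A2 at 20, B at 80: shares 0.1915 and 0.0919, factor 2^(−0.0996) = 0.933. The ratio is 0.273 under the SAP rule against 0.292, so it is 6.7% lower.
- A2 at 5, B at 20: shares 0.1499 and 0.1915, factor 2^(0.0416) = 1.029. The ratio is 0.451 against 0.438, so it is 2.9% higher.

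Over the three SDs, the A2/B pairs 14/40, 20/80, 20/160 and 40/160 give a ratio 2% to 15% lower. The pairs 3/14, 3/20, 3/40, 5/14 and 5/20 give a ratio 2% to 13% higher.

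**Step 4: scale.** With 33 per group, the 95% interval for a ratio of two GMTs extends by a factor 2^(1.96 × SD × √(2/33)) each way: 1.65, 1.95 and 2.31 for the three SDs. A 20-point difference in shares moves the ratio by a factor of 1/0.871 = 1.15.

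**The case against.** **Direction.** A reader might infer that the rule biases the weaker-responding group more, and so overstates the deficit in A2 and inflates the rise from before to after vaccination. The documents do not support that. Results below the limit become LLQ/2 under either rule, so only results exactly at it matter, and a weak group may have few of these because most of its results lie lower still. Step 3 shows the reversal. Protocol 5.1.1.6 says that treated patients mounted reduced responses, influenza included, but gives no titers, so it does not settle which case applies.

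**The limit of 10 is inferred.** This stands. The cut-off of <10 belongs to the seroconversion definition and is never called an assay limit. A responder cut-off and a substitution rule need not agree, so the text alone does not contain a contradiction.

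**The ≤ sign may be deliberate.** If the laboratory stores results below the limit as the LLQ value, ≤ is what catches them, and a bare change to < would leave every such result unsubstituted. That is a good reason not to make the bare change. It does not rescue the rule: the coding is not stated, and with it a numeric comparison alone could not tell a measured result at the limit from one below it.

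**Little depends on it.** This largely stands. No hypothesis testing is planned (SAP 4.4). SAP 4.4.2.4 gives between-group differences with intervals only for the four influenza proportions, not for GMTs. It already urges caution because A2 was not formed at random. It states no substitution for the post:pre GMT ratio.

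**Conclusion.** The point holds as a minor error in a stated rule. As written, a result equal to the LLQ is treated as unquantified, halved in the all-values geometric mean and median, and excluded from the above-LLQ summaries. Where a share f of a group lies exactly at the limit, its GMT is multiplied by 2^(−f). That multiplier is exact; whether any HI results tie at the limit rests on the assumption of discrete readings with an LLQ of 10.

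Unequal shares distort groups or timepoints unequally, in a direction that cannot be fixed beforehand. The percentages for A2 against B describe what a reader would see on setting the two GMTs side by side; they do not refer to a planned estimate. The effect is modest against sampling error and limited to descriptive summaries. The primary tetanus responder endpoint and the influenza responder proportions have no stated substitution and are not affected.

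**What to change.** In SAP 4.3.7 and 4.4.1:
- Impute LLQ/2 only for results reported as below the LLQ. If the laboratory stores such results as the LLQ value, identify them by its below-limit flag, not by numeric comparison.
- Keep a measured result equal to the LLQ at its value.
- Use < LLQ and ≥ LLQ for the counts and for the subset geometric means, intervals and medians.
- State each assay's LLQ and how results below it are coded. If the HI LLQ is confirmed as 10, <10 becomes 5 and a titer of 10 stays 10.
- In SAP 4.4.2.4, say whether substituted values enter the post:pre GMT ratio and the fold rises.

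The cost is a few words in the SAP, a changed condition in the programs, and confirmation of the coding with the laboratory. A count of measured results equal to the LLQ, by assay, group and visit, would show at once whether any table changes.
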